4.2 SCIENTIFIC RATIONALE FOR STUDY DESIGN

Evidence in the literature¹¹⁻¹⁶ support the hypothesis that an IVR audiovisual stimulation approach using the binocular 3D multiple object tracking (3D-MOT) in the head-mounted display (HMD) Oculus Go/Quest could provide a suitable visual rehabilitation approach for children with visual field defects. The central features of the 3D-MOT closely match attentionally demanding real-life situations^{17,18}. The setup of the task is highly dynamic as the objects change their location over time, requiring a continuous deployment of visual attention to avoid confusions between the objects¹⁸. 3D-MOT can be combined with fixation (still or tracking) while allocating the attention in the visual space to track other moving objects (covert attention) with the peripheral retina, a situation found in complex dynamic scene recognition^{18,19}. 3D-MOT stimulation programs displayed on monitors or TV screens have been shown to increase brain capacity for complex processes such as anticipation, eye-tracking, field of view and even decision-making in healthy and pathological participants²⁰⁻²². Recent work in low-vision patients with homonymous hemianopsia indicated a beneficial effect of audiovisual 3D-MOT IVR stimulation program using the Oculus Go on contrast sensitivity, fixation stability, reading speed and field of vision²³.

There are currently no visual rehabilitation strategies for children presenting visual field defects consecutive to a brain tumor or its treatment. The use of IVR in children aged 4-10 years old has not raised any safety concerns²⁴. Moreover, by using the remotely controlled and stand-alone Oculus Go, our strategy favors a home-based stimulation program which will increase compliance and adherence to the program.

4.3 END OF STUDY DEFINITION

A participant is considered to have completed the study if he or she has completed all phases of the study including the last visit or the last scheduled procedure shown in **Section 1.3, Schedule of Activities (SoA)**. The duration of participation for each individual participant who completes all study visits will be 7 months.

The end of the study is defined as completion of the last visit or procedure shown in the SoA in the trial globally. It is estimated that it will take 24 months from when the study opens to enrollment until the end of the study.

5 STUDY POPULATION

Male and female patients > 8 years-old with diagnosed homonymous hemianopsia with no prior visual rehabilitation interventions.

5.1 INCLUSION CRITERIA

In order to be eligible to participate in this study, an individual must meet all of the following criteria:

1. Homonymous hemianopsia
2. Male and female.
3. > 8 years old
4. Interpupillary distance ≥ 56 mm

5. 5. BCVA > 20/20
6. Ability to follow the visual and auditory stimuli and training instructions.
7. Home Wi-Fi access.

5.2 EXCLUSION CRITERIA

An individual who meets any of the following criteria will be excluded from participation in this study:

1. Ocular diseases
2. Both eyes with media opacity that impairs microperimetry testing.
3. Inability to perform during testing and training.
4. Consumption of psychoactive drugs.
5. 3 consecutive VRIFE scores < 25 at inclusion.
6. History of vertigo or dizziness
7. Prior vision rehabilitation interventions.

5.3 LIFESTYLE

Psychoactive drugs consumption is not permitted (including medicinal cannabis).

5.4 SCREEN FAILURES

Screen failures are defined as participants who consent to participate in the clinical trial but are not subsequently randomly assigned to the study intervention or entered in the study. A minimal set of screen failure information is required to ensure transparent reporting of screen failure participants. Minimal information includes demography, screen failure details and eligibility criteria.

Individuals who do not meet the criteria for participation in this trial (screen failure) because of a inability to follow the visual and auditory stimuli and training instructions may be rescreened after 4 weeks to a maximum of 3 times. Rescreened participants should be assigned the same participant number as for the initial screening.

5.5 STRATEGIES FOR RECRUITMENT AND RETENTION

[name] and [name] will identify potential participants among their patients at the Hospital for Sick Children. Drs. [name] and [name] will make initial contact with potential participants. We will identify patients with homonymous hemianopia for a total of 10 participants. We will ensure 5 patients had lesions involving the optic chiasm and 5 not involving the optic chiasm

6 STUDY INTERVENTION

6.1 STUDY INTERVENTION(S) ADMINISTRATION

6.1.1 STUDY INTERVENTION DESCRIPTION

The device used is the commercially available virtual-reality, standalone, head mounted display Oculus Quest 2 (Facebook Technologies, Qualcomm, Xiaomi). There are currently 34 clinical trials registered on Clinicaltrials.gov using the Oculus Go or Quest: 12 in the US and 4 in Canada. [name] lab (co-

investigator) is currently running a clinical study using the Oculus Quest 2 in elderly patient with macular degeneration (NCT04685824, UHN REB approval 20-6143). The application uploaded in this device is the NeurofyResearch application, developed and owned jointly by UHN and Neuropowertrain (Research and Collaboration Agreement). It is a modified version of the Neurofy application, owned by Neuropowertrain, used for perceptual/cognitive training in professional athletes.

[figure not shown]

Figure 2: representation of the 3D-MOT stimulation procedure:

1. 8 spheres appear in the headset **2.** One sphere is cued (red) and returns to yellow after 5 seconds. **3.** All spheres start moving randomly for 20 seconds. **4.** After 20 seconds, the spheres stop moving. **5.** The patient must select using laser pointer (white) the ball corresponding to the cued one. **6.** The result is displayed corresponding to either a hit (correct selection) or a miss (wrong selection). Sequence returns to 1. for the next trial.

Audiovisual IVR stimulation procedure

This procedure corresponds to:

- 1 session every 2 days (± 1 day) for 4 weeks.
- 1 session = 3 blocks of 15 audiovisual stimulation tasks (2 min break between each block).
- 1 task = 20 seconds audiovisual IVR stimulation (3D-MOT + correlated sound).

The audiovisual stimulation task (the *NeurofyResearch* application) involves the 3D multiple-object-tracking (3D-MOT) paradigm composed of 8 high-contrast spheres which features are adapted to the visual ability of low-vision patients (luminosity = 100cd/m², size = 1.57° of visual angle). The spheres move for 20 seconds following random linear paths, bouncing on one another and on the walls of a virtual 3D cube when collisions occur. The overall span of the movement of the spheres covers 80° and 60° of horizontal and vertical visual angle respectively. The initial speed of the spheres is adjustable, from 3°/s. to 240°/s. and determined during the inclusion visit (figure 2).

6.1.2 DOSING AND ADMINISTRATION

The patient, comfortably seated, is asked to track the moving cued target (1 sphere) among moving distractors (7 spheres) for 20 seconds. A spatial sound (50Hz, 25-65dBHL) is correlated to the movement of the cued target. After 20 seconds, the movement stops and the patient is asked to select, using a laser pointer, the cued sphere among the distractors (mark-all procedure). If the selection is correct (i.e. corresponding to the cued target) a positive feedback sound is provided and the speed of the spheres in the next trial is increased by 0.05log. If the selection is incorrect (i.e. corresponding to a distractor) a negative feedback sound is provided and the speed of the spheres in the next trial is decreased by 0.05log (adaptive simple up-down staircase). After each block of 5 minutes, the system sends data relative to the time spent performing the tasks (primary outcome) to our dedicated and secured laboratory computer through Wi-Fi and resets. This procedure takes approximately 1 minute and can be stopped by the patient for a longer break in between blocks if necessary (time of the break is recorded). After 3 blocks, the system

stops and goes on stand-by mode until the next session. The next session (to be performed 48 hours later) will be automatically uploaded in the device and will be initiated by the patient.

Audiovisual IVR stimulation, 1 session every 2 days for 4 weeks (15 sessions). 1 session = 3 x 5 minutes audiovisual stimulation.

6.2 PREPARATION/HANDLING/STORAGE/ACCOUNTABILITY

6.2.1 ACQUISITION AND ACCOUNTABILITY

The study team will provide each participant a Virtual reality headset (Oculus Quest 2) to take home and perform the visual training intervention. At study completion, the participants will return the headset to the study team for cleaning and storage procedures as developed by IPAC.

6.2.2 PRODUCT STORAGE AND STABILITY

Standalone, virtual-reality, head-mounted display Oculus Go/Quest 2.

To keep your Oculus Quest 2 safe, follow these tips:

- To avoid damaging your lenses and display, keep your Quest 2 away from direct sunlight. Your headset can be permanently damaged from less than a minute of exposure to direct sunlight.
- To avoid scratching your lenses, keep your Quest 2 away from sharp objects (example: cable tips, keys).
- To avoid damaging your headset or straps, be gentle when adjusting your headset and tightening the straps.
- Do not use or wear your headset while connected to the power adapter or charging.

To avoid general damage:

- Don't leave your Quest 2 in extremely hot locations (example: inside of a car).
- Don't leave your Quest 2 near heat sources (example: furnace).
- Don't leave your Quest 2 near pets or small children.
- Don't eat, drink or smoke near your Quest 2.
- Secure your Quest 2 in a safe place when you're not using it.

6.3 MEASURES TO MINIMIZE BIAS: RANDOMIZATION AND BLINDING

There will be no measure to minimize bias as this study is a feasibility study testing the adherence and compliance to the visual rehabilitation procedure.

6.4 STUDY INTERVENTION COMPLIANCE

This corresponds to the primary objective and will be monitored in real-time after each blocks of tasks.

6.5 CONCOMITANT THERAPY

Supportive care will be administered as needed in accordance with SickKids standard clinical practices. Medications to be reported in the Case Report Form (CRF) are concomitant prescription medications, over-the-counter medications and supplements. Use of psychoactive drugs is prohibited while participants are on the study intervention.

7.1 DISCONTINUATION OF STUDY INTERVENTION

The participant, or the participant's legally acceptable representative(s) can withdraw consent for participation in the study at any time without prejudice. The investigator can withdraw a subject if, in his or her clinical judgment, it is in the best interest of the subject.

7 DISCONTINUATION AND WITHDRAWAL

Discontinuation from visual training does not mean discontinuation from the study, and remaining study procedures should be completed as indicated by the study protocol. If a clinically significant finding is identified (including, but not limited to changes from baseline) after enrollment, the PI or qualified designee will determine if any change in participant management is needed. Any new clinically relevant finding will be reported as an Adverse Event (AE).

Withdrawn patient will go for a final visit at the clinic with primary and secondary outcome assessment. Primary outcomes (adherence, VRISE scores, retention) collected until the withdrawal date will be analyzed. Secondary outcomes (BCVA, fixation stability, contrast sensitivity, reading speed, visual fields and quality of life) will be assessed during final visit and analyzed.

7.2 PARTICIPANT DISCONTINUATION/WITHDRAWAL FROM THE STUDY

Participants are free to withdraw from participation in the study at any time upon request.

An Investigator may discontinue or withdraw a participant from the study for the following reasons:

- Withdrawal of informed consent (participant or parent/guardian withdraw for any reason)
- If any clinical Adverse Event (AE), laboratory abnormality, or other medical condition or situation occurs such that continued participation in the study would not be in the best interest of the participant
- Significant study intervention non-compliance
- Disease progression which requires discontinuation of the study intervention
- Requirement of prohibited concomitant medication(s) that requires discontinuation of the study intervention
- Three consecutive VRISE scores < 25 during the 4-week home-based audiovisual IVR stimulation procedure will terminate the investigational intervention.

The reason for participant discontinuation or withdrawal from the study will be recorded in the study "Study termination" CRF. Participants who sign the informed consent form and are randomized but do not receive the study intervention may be replaced. Participants who sign the informed consent form, and are randomized and receive the study intervention, and subsequently withdraw, or are withdrawn or discontinued from the study, will be replaced. The data from participants who are withdrawn or discontinued from the study will be used in the analysis unless the participant requests otherwise.

The Oculus Quest 2 device will be turned off remotely preventing its use by the participant. The participant will return the Oculus Go/Quest including all the equipment (storage box, batteries, remote control, straps) at the final visit.

Withdrawn patients will be replaced to reach a total number of 10 evaluable patients.

Patients will be contacted after 24 hours by phone or email and evaluated for residual virtual-reality symptoms and effects (VRISE questionnaire).

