4 STUDY DESIGN

4.1 OVERALL DESIGN

We hypothesize that the home-based audiovisual 3D-MOT IVR stimulation program can be performed by HH pediatric patients and that this program will improve visual perception, reading speed and quality of life. For our trial design, we used the Pragmatic-Explanatory Continuum Indicator Summary (PRECIS-2) instrument, initiated and supported by the NIH Pragmatic Trials Collaborative Project to generalize knowledge about the conduct of pragmatic research. PRECIS-2 takes the innovative approach of translating ratings on nine domains related to trial design to a readily understood wheel format that communicates where the trial design falls on the explanatory (scored 1) - pragmatic (scored 5) continuum^{30,31} (Figure 1). All eligible patients in our study will be patients from care center at Sickkids, Toronto recruited through regular appointments made at the clinic (eligibility – recruitment). The setting of the trial corresponds to clinical visual care centers (setting). Information sheets will be given out to participants. Provider expertise corresponds to low-vision care center (organization). The group of patient will follow the study protocol from home, which can be usual practice in visual rehabilitation procedures. The delivery of the intervention is flexible with IVR stimulation every 2 days (± 1 day) at any time during the day (delivery). Adherence will be evaluated every 2 days; patients are free to “not-comply” and there will be no measures to improve adherence (adherence). Follow up of the primary outcome (adherence to the protocol) will be sent automatically through Wi-Fi to a dedicated and secured laboratory computer in real-time after each session. Secondary outcome will be assessed at the final visit after 4 weeks (follow-up secondary outcome at 1 month and 6 months). An Intention-to-treat will be performed for the analysis of the primary outcome (primary analysis). According to the PRECIS-2-wheel results (Figure 1), we propose an **interventional, pragmatic, single center pilot study** to assess **the feasibility and potential effectiveness of IVR stimulation in pediatric population of homonymous hemianopia patients**.

[figure not shown]

Figure 1: PRECIS-2 wheel indicating that our study is a pragmatic trial (scores >3).

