Primary outcome corresponds to the feasibility of the study in terms of adherence, retention rates and recruitment. We specified, a priori, 4 feasibility objectives for our pilot study to be considered successful:

1. $\geq 8/10$ patient (80%) completed the protocol.
2. IVR stimulation protocol is considered complete if the patient performed ≥ 12 sessions out of 15.
3. ≤ 3 consecutive VRISE score < 25 per patient during the treatment period.
4. ≤ 2 dropouts (20%) for cybersickness (discomfort symptoms experienced in VR)

Completion of the sessions will be monitored in real-time. After each block, a data sheet (.csv, 2 kb) containing device ID#, subject #, date/time, time to complete the task/block, number of tasks/blocks performed, total stimulation time, total duration of the session will be sent though Wi-Fi to a dedicated and secured laboratory computer in real-time (if no Wi-Fi access is available at the end of each block, data are stored in the device and sent as soon as Wi-Fi is again available – data storage capacity 500 Mo. No extra costs are incurred to the patients' Wi-Fi plan for sending data). Each session contains 3 data sheets. A session is considered complete when 3 blocks of 5 min stimulation are performed. If no data sheets are received on the lab's computer for a period of 3 consecutive days or missed/incomplete sessions are observed, the participant's parent will be contacted by phone and email to identify the cause (no Wi-Fi, Oculus Go malfunction, dropout) and appropriate action will be taken. Before and after each session, the participant will answer to the VRISE questionnaire (5 questions scored 1 to 7 using the Oculus Go). After the completion of the questionnaire, the detailed score will be sent though Wi-Fi to a dedicated and secured laboratory computer in real-time.

Secondary outcome corresponds to potential effectiveness of IVR stimulation measured by visual perception and quality of life assessed following standard procedures used in low-vision rehabilitation²⁷ and collected at the low-vision clinic by ophthalmologists. Endpoints will measure change from baseline at 2 and 4 weeks in:

- Best Corrected Visual Acuity, distance and near vision (ETDRS chart, Colenbrander chart).
- Mean fixation stability (MAIA micro-perimeter).
- Contrast sensitivity (FACT test).
- Points not seen – Humphrey full field 120 (HFA3, Zeiss)
- Points not seen – Esterman binocular field (HFA3, Zeiss)

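### Section 7.2 allows withdrawal, headset shut-off and replacement for undefined non-compliance, which is the primary outcome itself, and the fixed 8/10 criterion is not reconciled with the intention-to-treat population once anyone is replaced

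*Combined protocol and SAP*

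**What the plan says.** **Adherence is the outcome.** Sections 3 and 4.1 make adherence to the home sessions, with retention, part of the primary feasibility outcome. Section 6.4 says of compliance: "This corresponds to the primary objective and will be monitored in real-time after each blocks of tasks". Section 4.1 adds: "Adherence will be evaluated every 2 days; patients are free to" not comply, and no measures are planned to improve adherence.

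**Adherence is also a ground for removal.** Among the reasons for which an investigator may withdraw a participant, Section 7.2 lists "Significant study intervention non-compliance". No section gives a number of sessions or days. The same section continues: "The Oculus Quest 2 device will be turned off remotely preventing its use by the participant", and "Withdrawn patients will be replaced to reach a total number of 10 evaluable patients". For children who have already received the intervention, replacement is mandatory.

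**Success criterion.** Sections 4.1 and 9.1, and the primary-outcome text in Section 9.4 (printed under heading 9.4.3), require at least 8/10 patients (80%) to complete the protocol. Complete means at least 12 of 15 sessions.

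**Analysis population.** Section 4.1 states: "An Intention-to-treat will be performed for the analysis of the primary outcome (primary analysis"). Section 9.4 repeats intention-to-treat directly above the criteria, and Section 9.3 defines that population as all patients registered. Section 7 keeps the data of withdrawn children: "Primary outcomes (adherence, VRISE scores, retention) collected until the withdrawal date will be analyzed". Section 7.2 requires the reason for withdrawal to be recorded.

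**The concern.** The pilot asks how many children will do at least 12 of 15 sessions at home. A child who misses sessions is part of the answer. Here missed sessions can trigger removal, at the discretion of an investigator who sees adherence in real time in an open-label study, and removal triggers a replacement. This differs from withdrawal for safety, disease progression or loss of consent, where the trigger is not the outcome being measured.

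Two things are at stake. First, the verdict can depend on which base is used: the 10 that Section 7.2 refills, or everyone registered. Second, shut-off ends the child's session and VRISE record, so the child's own result is settled by the decision and no longer by the child's behaviour.

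**Working it through.** **Inputs from the documents.** 10 patients (9.2); at least 8/10 = 80% (4.1, 9.1, 9.4); at least 12 of 15 sessions (same places); replacement to 10 evaluable (7.2); intention-to-treat means all registered (9.3). The plan gives no expected completion, attendance or withdrawal rate.

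**Step 1. The plan's own figures.** 8/10 = 0.80, 12/15 = 0.80, and 2/10 = 0.20 for the cybersickness dropout criterion. All reproduce, and all presuppose exactly 10 children.

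**Step 2. The two bases after replacement.** Let w non-completers be withdrawn and replaced. The registered number is N = 10 + w. The number needed for 80% of N is 0.8N rounded up. The most completers possible is 10, because the w withdrawn children did not complete.

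| w | N | 8 completers, 10 evaluable | 8 completers, all registered | Needed for 80% of N | Best possible on N |
|---|---|---|---|---|---|
| 0 | 10 | 80% | 80% | 8 | 100% |
| 1 | 11 | 80% | 8/11 = 72.7% | 9 (8.8) | 10/11 = 90.9% |
| 2 | 12 | 80% | 8/12 = 66.7% | 10 (9.6) | 10/12 = 83.3% |
| 3 | 13 | 80% | 8/13 = 61.5% | 11 (10.4) | 10/13 = 76.9% |

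From the first replacement, 8 completers pass on one base and fail on the other. From the third, the registered base cannot reach 80% at all, while the evaluable base is unaffected. This step needs no assumption about rates.

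**Step 3. What shut-off does to one child.** Completion allows at most 3 missed sessions.
- A child who has missed 4 can reach at most 11, so shut-off changes nothing on completion.
- A child who has missed 2 of the first 6 has done 4 and needs 8 of the remaining 9. If attendance stays at 4/6, the chance is 9(2/3)^8(1/3) + (2/3)^9 = 0.117 + 0.026 = 0.143. If attendance rises to 0.8, it is 9(0.8)^8(0.2) + 0.8^9 = 0.302 + 0.134 = 0.436. After shut-off it is 0.
- The record lost for this child is at most 15 − 6 = 9 sessions and 18 VRISE scores (one before and one after each session). At 4/6 attendance the expected loss is 6 sessions and 12 scores.

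**Step 4. Direction of the effect (illustration only).** Assume each other child, and any replacement, completes with probability p = 0.8 (range 0.7 to 0.9), independently. Take the child with 2 of 6 missed and c = 0.143.
- Child stays: c·P(Bin(9, 0.8) ≥ 7) + (1 − c)·P(Bin(9, 0.8) ≥ 8) = 0.143 × 0.738 + 0.857 × 0.436 = 0.479.
- Child replaced, judged on 10 evaluable: P(Bin(10, 0.8) ≥ 8) = 0.678, a change of +0.20 (+0.13 to +0.20 over the range).
- Child replaced, judged on 11 registered with 9 needed: P(Bin(10, 0.8) ≥ 9) = 0.376, a change of −0.10 (−0.06 to −0.10 over the range).

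The same decision raises the chance of success on one base and lowers it on the other.

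**Step 5. Systematic use of the clause, 10-evaluable base only (illustration).** If a share f of non-completers is replaced, completion among the evaluable is q = p/(p + (1 − p)(1 − f)). With p = 0.6 and f = 0.5, q = 0.6/0.8 = 0.75, and P(at least 8 of 10) rises from 0.167 to 0.526. With f = 1, q = 1 and the criterion cannot fail, whatever p is.

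**The case against.** The strongest reply is that the plan already answers the question. It names intention-to-treat for the primary outcome, defines it as all registered, keeps withdrawn children's data, and prints 80% beside 8/10, so 9 of 11 or 10 of 12 follows naturally. The word evaluable appears in Section 7.2 as a recruitment target and is never tied to the success criterion. Withdrawal is permissive, reasons are recorded, and the stated response to missed sessions in Section 4.1 is to contact the parent and find the cause ("no Wi-Fi, Oculus Go malfunction, dropout) and appropriate action will be taken"). Nothing suggests that 2 missed sessions of 6 would count as significant.

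Much of this stands, and it limits the point. Three stronger readings are tempting and are not supported:
- A reader might infer that the criterion has no denominator. It has two: a fixed 10, and the registered population. The defect is that they are not reconciled.
- A reader might infer that the plan inflates feasibility. Inflation arises only if the 10 evaluable are the base. On the registered base, replacement lowers the chance of success in Step 4.
- A reader might infer that each such withdrawal takes 10 points off retention. The plan gives no retention formula, and Section 7 says that stopping training does not mean leaving the study.

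The open-ended action promised in Section 4.1 is not a defect in itself and needs no change for this point.

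The reply does not remove the conflict. No sentence says how 8/10 applies when 11 or more are registered. Analysing data up to withdrawal cannot recover sessions that the child was prevented from doing. Adherence is still both the outcome and a ground for removal.

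**Conclusion.** The point holds in this form: an undefined, outcome-driven withdrawal rule with shut-off and mandatory replacement sits beside a fixed 8/10 that is not reconciled with the stated intention-to-treat population. The conflict in bases follows from the documents alone: with 8 completers and two non-completers replaced, the result is 80% or 66.7%; with three replaced, 80% is out of reach on the registered base. The truncation applies on either base, but affects completion only for a child who could still reach 12 sessions.

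The probabilities in Steps 3 to 5 rest on assumed attendance, completion and replacement rates. They show that the distortion can run in either direction; they do not predict that it will occur. The clause may never be used. The change is still worth making before enrolment, because with 10 children one discretionary decision can settle the verdict.

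**What to change.** 1. **Section 7.2.** Delete non-compliance as a reason for withdrawal. State that low adherence alone neither ends device access before day 28 nor triggers replacement.
2. **Sections 4.1, 9.1 and 9.4 (primary outcome).** State that the completion criterion is at least 80% of all registered children, using the definition in Section 9.3, for example 9 of 11 or 10 of 12. State that any child withdrawn before 12 sessions counts as a non-completer, and that a replacement does not remove that child from the denominator.

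Two details should be settled in the same sentence. All registered includes children who were registered but never treated; if the sponsor prefers treated children as the base, the plan should say so now. It should also say how a child is counted whose family asks that the data not be used, an exception that Section 7.2 allows.

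The cost is protocol wording, a headset that stays with a non-adherent child until day 28, and a reported completion rate that may be slightly less favourable.

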8.2.2 DEFINITION OF SERIOUS ADVERSE EVENTS (SAE)

An Adverse Event (AE) is any untoward medical occurrence associated with the use of an intervention in a study participant, which does not necessarily have a causal relationship with the intervention. An AE can therefore be any unfavourable and unintended sign (including an abnormal laboratory finding), symptom or disease temporally associated with the use of the intervention, whether or not considered related to the investigational intervention.

Stable chronic conditions which are present prior to entry in the study and do not worsen are not considered AE. These pre-existing conditions will be documented in the participant's medical history.

AEs will be the primary safety endpoints. Known AEs induced by IVR stimulation are nausea, dizziness and disorientation. The severity of these AEs will be scored using the validated VRISE questionnaire. A VRISE score < 25 is considered as an AE. Three (3) consecutive VRISE scores < 25 will lead to the withdrawal of the study.

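### Withdrawn patients are replaced up to 10 undefined evaluable patients, so after one replacement the 8/10 (80%) completion criterion can pass on one denominator and fail on the other

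*Combined protocol and SAP*

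**What the plan says.** **Replacement.** Under section 7.2, a participant who has received the intervention and then withdraws or is withdrawn will be replaced. No upper limit is given, and the target is stated as "Withdrawn patients will be replaced to reach a total number of 10 evaluable patients". One ground on which the investigator may withdraw a participant is "Significant study intervention non-compliance". Section 8.2 adds a cybersickness route: "Three (3) consecutive VRISE scores < 25 will lead to the withdrawal of the study".

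**Data of withdrawn patients.** Section 7.2: "The data from participants who are withdrawn or discontinued from the study will be used in the analysis unless the participant requests otherwise". Section 7: "Primary outcomes (adherence, VRISE scores, retention) collected until the withdrawal date will be analyzed".

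**Criteria.** Sections 4.1, 9.1 and 9.4 give the same list. Criterion 1 requires at least 8/10 patients (80%) to complete. Criterion 2 defines completion as at least 12 of 15 sessions. Criterion 4 allows at most 2 dropouts (20%) for cybersickness. Section 9.2 plans 10 patients.

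**Population.** Sections 4.1 and 9.4 call for ITT analysis of the primary outcome, and section 9.3 defines ITT as everyone registered. Section 9.3 uses evaluable only for the safety population, meaning registered patients with at least one session.

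**The concern.** The count 8/10 and the figure 80% are the same rule only at N = 10. Each replacement of a registered patient takes the ITT population above 10, and nothing says how criterion 1 is then read. The safety meaning of evaluable cannot be the one intended in section 7.2: a treated patient who withdraws has already had a session, would already be evaluable, and would need no replacement.

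Adherence and retention are primary measures here. A child withdrawn for non-compliance or cybersickness before session 12 is a feasibility failure. Judging 8/10 on the 10 patients left after replacement would take such failures out of the denominator and put new chances of success in their place. The study is open-label and adherence data arrive in real time, so an open rule could also be settled after the results are known.

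**Working it through.** **Inputs from the documents.** Threshold 8/10 (80%), completion at 12 of 15 sessions, and the cybersickness limit of 2 (20%), all from 9.1; planned N of 10 from 9.2; ITT as all registered from 9.3; replacement to 10 evaluable from 7.2.

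**The plan's own figure.** 8/10 = 0.80, so count and percentage agree at N = 10.

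**Thresholds after replacement.** Completers needed for 80% of N registered = 0.8N rounded up. Cybersickness dropouts allowed at 20% = 0.2N rounded down.

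| Registered N | Completers needed for 80% | Completer counts of 8 or more that miss 80% | Dropouts allowed at 20% |
|---|---|---|---|
| 10 | 8 | none | 2 |
| 11 | 9 | 8 | 2 |
| 12 | 10 | 8, 9 | 2 |
| 13 | 11 | 8–10 | 2 |
| 14 | 12 | 8–11 | 2 |
| 15 | 12 | 8–11 | 3 |

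A patient who withdraws before 12 sessions adds no completer, so at most 10 completers can arise if all withdrawals are early. Counts above 10 need someone who completed and then withdrew.

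**One replacement.** The replaced patient did fewer than 12 sessions, 8 of the other 10 complete, and 2 stay in the study without completing.
- Evaluable: 8/10 = 80%, pass.
- Registered: 8/11 = 72.7%, fail (9/11 = 81.8% would pass).
- With 7 or fewer completers both readings fail; with 9 or more both pass.
- If the replaced patient had already done 12 or more sessions, the registered figure is 9/11 and both readings pass.

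**Three early withdrawals.** Even 10/10 evaluable is 10/13 = 76.9% of registered, a fail.

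**How often the readings could differ (assumed rates only).** The documents give no completion or withdrawal rate. Suppose each registered patient completes with probability c, withdraws before 12 sessions with probability w, and otherwise stays without completing. Registration continues until 10 have not withdrawn early.
- Evaluable reading: P(X ≥ 8), X ~ Bin(10, c/(1−w)).
- Registered reading: N = 10 + W, where W is the negative binomial number of early withdrawals; pass if X ≥ 0.8N.
- Passing at 80% of registered implies passing the evaluable reading, so P(split) is the difference.

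| c / w / stay | Evaluable | 80% of registered | Split on criterion 1 | Split with at most 2 early withdrawals |
|---|---|---|---|---|
| 60 / 30 / 10 | 0.838 | 0.102 | 0.736 | 0.110 |
| 60 / 10 / 30 | 0.299 | 0.144 | 0.155 | 0.122 |
| 80 / 10 / 10 | 0.909 | 0.618 | 0.292 | 0.191 |
| 90 / 5 / 5 | 0.987 | 0.910 | 0.077 | 0.058 |

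The last column applies if every early withdrawal is for cybersickness. Three or more then fail criterion 4 by count (3 > 2) and by percentage (3/13 = 23.1%, 3/14 = 21.4%), so the study is not feasible however criterion 1 is read. If none is for cybersickness, criterion 4 gives no such protection and the fourth column stands. Mixed causes lie between.

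**The case against.** The strongest reply is that the plan already answers the question. ITT is assigned to the primary outcome, ITT is defined as all registered, and withdrawn patients' data are kept. Criterion 1 is a ratio written twice, never a bare 8, and the sentence on 10 evaluable patients sets a recruitment target, not an analysis set. This largely stands: the text favours all registered patients. It does not close the gap, because the written denominator is 10, the ITT denominator exceeds 10 after any replacement, and the only other 10 in the text is the evaluable group. Section 7.2 also lets a participant ask that their data not be used, without saying how that person is counted.

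It is also fair that not every non-completer is replaced. Section 7 says "Discontinuation from visual training does not mean discontinuation from the study", and section 4.1 says "there will be no measures to improve adherence", so some will stay and count as failures on either reading. Retention would be reported too, so withdrawals would be visible.

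A reader might infer that the whole feasibility verdict flips with the denominator, or that a split is likely. The documents support neither. Success requires all the criteria, and criterion 4 already fails the study in many cases with several cybersickness withdrawals. The largest split probability, 0.736, needs 60% completion, 30% early withdrawal and unlimited replacement, with an average of 10/0.7 = 14.3 registered at a single centre planning 10. A reader might also infer that criterion 4 has the same problem. Its count and percentage give the same verdict for N = 10 to 14 and part only at 3 dropouts with N of at least 15.

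**Conclusion.** The point holds for criterion 1. The replacement rule, the undefined evaluable group and the fixed 8/10 together allow early withdrawals to leave the denominator of a criterion meant to capture them, and any such reading is biased towards success. The 8/10 against 8/11 = 72.7% example needs no assumed rate. With one early withdrawal the disagreement is confined to exactly 8 completers; with three, no result among the 10 evaluable patients reaches 80% of registered. Across the four illustrative scenarios the chance of a split on criterion 1 runs from 0.077 to 0.736. It falls to between 0.058 and 0.191 if all early withdrawals are for cybersickness, because criterion 4 then decides the remaining cases. These probabilities rest wholly on assumed rates and on replacement without limit. The ambiguity should be fixed before results are seen.

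**What to change.** - **Sections 4.1, 9.1 and 9.4:** state criterion 1 as at least 80% of all registered (ITT) patients performing at least 12 of 15 sessions, whatever the final N. Count a patient who withdraws before 12 sessions as a non-completer, and add replacements to the denominator.
- **Section 7.2:** define evaluable for the replacement target, and say that replacement does not remove the withdrawn patient from criterion 1. State how a patient who asks for data not to be used is counted.
- **Criterion 4:** for consistency, state it on the same denominator. This changes no verdict for N = 10 to 14.

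The cost is wording only, with no extra patients. The reported completion rate may be less favourable than one based on 10 evaluable patients.
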